3.4 Outcomes

3.4.1 Primary Outcome Measure:

Outcome Measure	Measure Description	Time Frame
Changes of nutritional status from the baseline to the end of treatment and differences between the intervention group and the placebo group.	Nutritional status of the patient is defined as the results of physical examination and SGA-7 rating scale.	From the baseline to the end of treatment.
Changes of quality of life from the baseline to the end of treatment and differences between the intervention group and the placebo group.	Quality of life of the patient is defined as the scores of gastrointestinal symptom rating scale (GSRS), kidney disease life quality scale (TM-SF36) and enervation frailty scale (EFS).	From the baseline to the end of treatment.

3.4.2 Secondary Outcomes:

Outcome Measure	Measure Description	Time Frame
Changes of enterogenous urotoxin level from baseline to the end of treatment and difference between the intervention and placebo group.	Enterogenous urotoxin level is defined as the serum level of IS, PCS and TMAO. The levels of serum IS, PCS and TMAO will be measured by mass spectrometry.	From the baseline to the end of treatment.

Changes of intestinal flora structure from the baseline to the end of treatment, and the difference between the intervention group and the placebo group.
	
The structure of intestinal flora will be measured by the V3-V4 region of 16S rDNA with MiSeq PE300 sequencing platform for high-throughput analysis and described by number of the flora.
	
From the baseline to the end of treatment.

Changes of routine biochemical indicators from the baseline to the end of treatment, and differences between the intervention group and the placebo group.
	
The routine biochemical indicators include serum creatinine, urea nitrogen, albumin, prealbumin, hemoglobin, serum calcium, blood phosphorus, total parathyroid hormone, serum potassium, carbon dioxide, C-reactive protein, ferritin, transferrin saturation.
	
From the baseline to the end of treatment.

Changes of dietary intake from the baseline to the end of treatment, and the difference between the intervention group and the placebo group.
	
Dietary intakes of the patients will be described by the diet record.
	
From the baseline to the end of treatment.

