3.8 Statistical Analysis

Descriptive statistics for continuous variables will include questionnaire score, anthropometric and biochemical indicators, fecal flora structure and urotoxins level. They will be expressed as mean \pm standard deviation and median. Analysis of categorical variables will include frequency and percentage.

In analytical statistics, the distribution type of data will be initially considered when we determine the reference range, and then we will calculate the unilateral lower limit P5. We will compare the distribution of the variables between the normal population and the patients in the two groups with Independent t test, Chi-square test /Fisher exact test, one-way ANOVA and non-parametric analysis. We will analyze the relationship between exposure and outcome with Logistic regression and Cox

regression, including univariate and multivariate regression. In multivariate regression analysis, the selected variables include important general clinical data, the variables clearly associated with the outcome, and the variables analyzed as $P < 0.1$ in univariate regression.

Statistical analyses will be performed using Statistical Package for Social Science (SPSS) for Windows version 23.0 (SPSS Inc. Chicago, IL). Statistical mapping will be performed using GraphPad Prism v.8 (La Jolla, CA, USA) and R 4.1.0 (The R Foundation, Vienna, Austria). Sample size estimation will be performed using PASS 2021 (UT, USA).

$P < 0.05$ is considered statistically significant. All confidence intervals are stated at the 95% confidence level.

4. Subject Protection

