9.1 Appendix A. SGA 7 Scale

SGA 7 Scale: 6-7 points are classified as very mild malnutrition to good nutrition; 3-5 points are classified as mild to moderate malnutrition; 1-2 points are classified as severe malnutrition.

Subjective Comprehensive Nutrition Assessment Form

Items	Instructions	Score
-------	--------------	-------

Change of Weight (Measured in % compared to the weight 6 months earlier) Dry weight 6 months ago: ___Kg Dry weight 2 months ago: ___Kg Current dry weight: ___Kg	+5% is normal 7 points: Body weight stable without change 6 points: There is a recent trend of weight loss >5 to 10% indicates a potential problem 5 points: Weight loss of 5 to 6% 4 points: Weight loss of 7-8% 3 points: Weight loss >10% >10% indicates serious problems 2 points: Weight loss, recent tendency to stabilize or slight change 1 point: Sustained weight loss	
Diet Based on daily intake of the patients and evaluate whether it meets the dietary recommendations	7 points: Normal amount 6 points: Decreased in recent days, but usually moderate 5 points: Continuous reduction, but moderate 4 points: Continue to decrease, sometimes moderate and sometimes not 3 points: Continued to decrease, but not a moderate amount 2 points: Continued to decrease, mostly very little food 1 point: Continued to decrease, but very little food	
Gastrointestinal Symptoms Loss of appetite, nausea, vomiting, diarrhea, etc. The frequency and duration of symptoms.	7 points: Asymptomatic 6 points: Symptoms are rare 5 points: One or more symptoms occur, but not daily 4 points: Appear more than one per day 3 points: Most symptoms appear daily 2 points: A day with almost all symptoms 1 point: Daily occurrence of all symptoms	
Ability of Daily Living (Compared to 6 months ago) Work, family, social	7 points: General condition 6 points: Worse than average, but not related to nutritional status 3-4-5 points: Worse than average, but related to nutritional status 2 points: Bedridden or wheelchair, related to nutritional status but can perform simple activities 1 point: bedridden, related to nutritional status but unable to perform simple activities	
Metabolic Stress	7-6 points: Only ESRD or (and) well-controlled DM 4-5 points: DM with infection/fever/peritonitis/poor control 1-2-3 points: Serious diseases such as ulcerative colitis with diarrhea	

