9.4 Appendix D. Enervation Frailty Scale (EFS)

Score: _____ /17				
		0 Point	1 Point	2 Points
Clock test (cognition)	1. Think of this pre-drawn circle as a clock. 2. Write the number down on the dial in the correct position. 3. Put the pointer in the "eleven ten" position.	No mistake	Mild mistake	Other mistake
General health state	How many times did you hospitalize in the past year?	0	1-2	>2
	How would you describe your overall health?	Very good & Good	Normal	Terrible
Functional independence	How many of the following activities do you need help? (Cooking, shopping, transportation, phone calls, housework, laundry, financial management, medication)	0-1	2-4	5-8
Social Support	When you need help, do you think there will be someone willing to help and able to meet your needs?	Often	Sometimes	Never
Medication	Do you take 5 or more pills a day?	No	Yes	
	Would you forget to take medicine?	No	Yes	
Nourishment	Did you lose any weight recently, such as your clothes becoming looser?	No	Yes	
Emotion	Do you often feel depressed?	No	Yes	
	Do you have trouble in controlling urinating when you don't want to urinate?	No	Yes	
Somatic function	Sit in the chair with your back and arms relaxed. Then, when I say "go," stand up and walk at a safe and comfortable pace to the mark on the floor (about 3 meters away), then return to your chair and sit down.	0-10s	11-20s	More than 20s, or unwilling to act, or need assistance to act

Evaluation: 0-5 points are defined as not weak; 6-7 points are defined as vulnerable; 8-9 points are defined as mild weakness; 10-11 points are defined as moderate weakness; more than 11 points are defined as severe weakness.

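### Protocol 3.8 assigns the exposure-outcome analysis, including its only multivariable models, to logistic and Cox regression, although 3.4 defines the outcomes as changes in scores or levels and no binary event is specified

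*Protocol*

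**What the plan says.** **Outcomes (Protocol 3.4).** For nutrition: "Nutritional status of the patient is defined as the results of physical examination and SGA-7 rating scale". For quality of life: "Quality of life of the patient is defined as the scores of gastrointestinal symptom rating scale (GSRS"; the sentence goes on to add the TM-SF36 and the EFS. What is to be compared is "Changes of quality of life from the baseline to the end of treatment and differences between the intervention group and the placebo group", and the nutrition outcome is worded the same way. The urotoxin and biochemical outcomes in 3.4.2 are likewise changes, in laboratory levels. No responder, threshold or event is defined.

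**Analysis (Protocol 3.8).** Questionnaire scores, biochemical indicators and urotoxin levels are classed as continuous variables. Distributions are to be compared "with Independent t test, Chi-square test /Fisher exact test, one-way ANOVA and non-parametric analysis". The effect of exposure is handled in a separate sentence: "We will analyze the relationship between exposure and outcome with Logistic regression and Cox" regression, in univariate and multivariate form. No linear regression or analysis of covariance is named.

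**Scales (Appendices A to D).** The SGA-7 has three bands, among them "6-7 points are classified as very mild malnutrition to good nutrition" and "3-5 points are classified as mild to moderate malnutrition". The EFS has five, for example "6-7 points are defined as vulnerable; 8-9 points are defined as mild weakness". The GSRS and TM-SF36 appendices give no bands.

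**The concern.** Ordinary logistic regression models the probability of a yes/no event. To apply it to the 3.4.1 outcomes, someone must first turn each score into an event, and neither 3.4 nor 3.8 says how. Three things follow wherever it is used.

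- **The estimate changes.** An odds ratio for being on one side of a cut is not the between-group difference in change that 3.4.1 asks for.
- **Information is lost.** A patient who improves without crossing the cut counts as unchanged.
- **The answer depends on the cut.** The appendix bands offer two boundaries for SGA-7 (2/3 and 5/6) and four for EFS (5/6, 7/8, 9/10 and 11/12). GSRS and TM-SF36 offer none.

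These are the only multivariable models in 3.8, so the adjusted treatment effect is what is affected. The Cox model in the same sentence has the same gap, since no time-to-event outcome is defined.

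**Working it through.** **1. Does the model fit the endpoint?**

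| Outcome | Type in 3.4 | Bands in appendix | Binary event in 3.4 or 3.8 |
|---|---|---|---|
| SGA-7 | change in score | 1-2, 3-5, 6-7 (level) | none |
| EFS | change in score | 0-5, 6-7, 8-9, 10-11, over 11 (level) | none |
| GSRS | change in score | none | none |
| TM-SF36 | change in score | none | none |
| Urotoxins, biochemistry | change in level | not applicable | none |

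The bands classify where a patient stands, not how far the patient has moved, and neither 3.4 nor 3.8 refers to them.

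**2. Inputs for the size.** Protocol 3.6 gives 30 per group and 20% dropout, so 30 × 0.8 = 24 completers per arm. It states no effect size, SD or power, so there is no power figure to reproduce. Assumed here: normal scores with equal SD, a true difference d = 0.8 SD, and two-sided alpha 0.05 (3.8 gives 0.05 without sidedness).

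**3. Continuous analysis.** Two-sample t test: noncentrality = d√(n/2) = 0.8 × √12 = 2.77 on 46 degrees of freedom. Power is 77.4%.

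**4. The same data cut into an event.** Let the event be a score on the favourable side of the cut, with control rate p0. The treated rate is p1 = Φ(Φ⁻¹(p0) + 0.8). Power is the exact sum over both binomials of all tables whose likelihood-ratio chi-square exceeds 3.841.

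| Cut | p0 | p1 | Logistic power | Points lost from 77.4% |
|---|---|---|---|---|
| Pooled median | 34.5% | 65.5% | 62.0% | 15.4 |
| Central | 20% | 48.3% | 56.3% | 21.2 |
| Central | 30% | 60.9% | 61.5% | 16.0 |
| Central | 50% | 78.8% | 57.1% | 20.4 |
| Off-centre | 10% | 31.5% | 47.8% | 29.6 |
| Off-centre | 70% | 90.7% | 46.8% | 30.6 |
| Off-centre | 80% | 95.0% | 40.7% | 36.7 |
| Off-centre | 90% | 98.1% | 28.6% | 48.8 |

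**5. Sensitivity.** With 30 per arm and d = 0.8, the t test has 86% power against 67-69% at the same central cuts. With 24 per arm and d = 0.6, it is 53% against 34-41%. A normal-approximation grid over d = 0.3 to 1.2, 20 to 30 per arm and control rates of 5% to 95% gives losses from about 4 to about 81 points.

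**6. EFS illustration.** Assume SD 3, control mean 6 to 8, a shift of 2.4 points (2.4/3 = 0.8 SD), 24 per arm and a continuity correction. Here the event is a score at or above the cut, so treatment lowers its rate.

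| Cut | Control rate | Logistic power |
|---|---|---|
| 6 or more | 57-80% | 56-62% |
| 8 or more | 31-57% | 47-60% |
| 10 or more | 12-31% | 34-47% |
| 12 or more | 3-12% | 4-34% |

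The true effect is the same in every row.

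**The case against.** **Continuous tests are also listed.** The t test used above as the benchmark is itself named in 3.8, and the section treats questionnaire scores as continuous. Nothing makes logistic regression the primary treatment comparison. This stands. A reader might infer that following 3.8 throws away about a third of the information in every primary score (a median split of a normal score keeps 2/π = 64%). The document does not support that: the loss arises only where logistic regression is used, and a seven-level SGA-7 rating is not a continuous normal score. The listed tests do not fill the gap, however. They give no adjusted estimate, and their sentence also brings in a normal population that the eligibility criteria do not provide for.

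**Ordinal logistic regression needs no cut-off.** For SGA-7 this is a fair reading, and the protocol does not say which form is meant. It is a less natural reading for a summed GSRS total or a serum level.

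**The statistical analysis plan may settle it.** A cut-off could be fixed there. One might therefore infer too much by saying that the cut-off will be chosen after results are seen. Protocol 3.1 does call the trial open labeled, but 5.1 plans coded subjects and blind analysis, so the most that can be said is that the protocol does not fix a cut-off. The mismatch remains: a plan that followed 3.8 with ordinary logistic regression would have to create an endpoint that 3.4 does not contain.

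**The trial is exploratory (3.6).** True. This tempers the severity but does not make the model fit the outcome.

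**Conclusion.** The point holds for the adjusted analysis. Protocol 3.8 ties exposure and outcome to models that need an event, while 3.4 defines changes in scores and levels and specifies no event. That conclusion needs no power calculation.

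The size is conditional. At 0.8 SD, normal scores and 24 completers per arm, central cuts lose about 15 to 21 points of power (77% down to 56-62%), and off-centre cuts with control event rates of 10% or 70-90% leave 29-48%. It would be wrong to infer one fixed loss for any cut-off: the figure moves with the cut, the effect size and the number of completers, and the protocol fixes neither the cut nor the effect. The calculations compare unadjusted tests, so they show the cost of cutting the score and do not predict the power of a particular adjusted model.

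This is a change that should be made, with a near-zero cost. It does not show that the unadjusted comparison is invalid.

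**What to change.** In Protocol 3.8, for the 3.4.1 scores and the continuous urotoxin and biochemical levels in 3.4.2, replace logistic regression with linear regression of the week-12 value on randomised arm, with the baseline value of the same measure as covariate. Regression of change from baseline on arm is an acceptable alternative. A model of the week-12 value on arm alone would not be enough, because it contains neither baseline nor change and so would not match 3.4.1. Week 12 is the appropriate time because group B moves to the active product afterwards.

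Report the group A minus group B mean difference with its 95% CI as the treatment-effect estimate. If a responder analysis is wanted, label it supportive and fix one cut-off per scale before data are seen. Remove Cox regression for these outcomes or name the time-to-event outcome it serves.

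Cost: a wording change, with no added patients, visits or measurements. The one downside is that an odds ratio is no longer the main adjusted measure.

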3.3.3.3 Treatment Period (1st to 12th Week)

Follow-up visits are scheduled at every 4 weeks in the treatment period. The following list summarizes the procedures for the treatment period:

- We should ask patients about any adverse events and changes in medication after last follow-up visit.
- We should record any change of dialysis prescription.
- We should record any problem of hemodialysis device, dialyzer and hemodialysis line.
- We should record the diet of patients in the 12th week.
- We should score the rating scales in the 12th week.
- We should perform the anthropometric measurements in the 12th week.
- We should collect the blood and stool samples for urotoxins and intestinal flora measurements in the 12th week.
- We should collect the results of recent routine blood test before dialysis of the patient in the 4th, 8th and 12th week.
- We should ensure whether the patient has still met the eligibility criteria. If so, supply the medicine at the original dose. If not, remove him/her from the group.

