3.5 Exposure

Metabolites of intestinal probiotics are those bioactive compounds produced by intestinal bacteria when they consume prebiotics, including short-chain fatty acid, lipolyaccharide, enzyme, exopolysaccharide, cell-free supernatant, inactivated probiotic bacteria or cell fragments (e.g. cell wall fragments, bacterial lysates, et al) and other metabolites (e.g. vitamins, amino acids, et al). Supplying exogenous

intestinal probiotic metabolites is one of the therapies for intestinal flora disorder. It can regulate intestinal flora, improve nutritional status, reduce serum levels of urotoxins and improve quality of life. Patients usually need 8-12 weeks to take the postbiotic product. Here is the introduction of postbiotic product.

The **Postbiotics** used in this study is Yi'en Yuan Honey Fermented Drink, which is made from water, edible brown sugar, and honey as raw materials. It is fermented by a mixture of plant lactic acid bacteria and coagulating Bacillus, and then inactivated at high temperature. The production of the product follows the GB7101 standard, and no live bacteria or related prohibited ingredients are detected in the finished product, which meets the food and beverage standards. According to *NJ-W22070721 Yi'en Yuan Honey Fermented Drink* and *SH-W23040315 Honey enzyme beverage test report*, the product includes carbohydrate 4.0-4.7g/100mL, potassium about 60.9mg/100mL, phosphorus about 2.8mg/mL. According to the concentration shown above, if you consume 150ml of the product a day, you will intake carbohydrate 6.0-9.1g, potassium 90mg, phosphorus 4.2mg, which is far lower than the daily intake of these substances from the diet and can be used for dialysis and diabetic patients. Since its launch in June 2021, no side effects have been reported.

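### The covariate rule in Protocol section 3.8 selects by association with the outcome and is not confined to pre-randomisation values, so the adjusted treatment estimate depends on the data and may lose part of the effect

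*Protocol*

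**What the plan says.** Section 3.8 plans regression for the main contrast: "We will analyze the relationship between exposure and outcome with Logistic regression and Cox" regression, both univariate and multivariate. For the multivariate models, "the selected variables include important general clinical data, the variables clearly associated with the outcome, and the variables analyzed as" P<0.1 in univariate regression. So there are three entry routes, two of them driven by the outcome data. No time point is attached to any route, and no other section supplies one.

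The same section also plans t tests, chi-square or Fisher tests, ANOVA and non-parametric comparisons. No analysis is named as primary.

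Many candidate variables are measured after randomisation. Section 3.3.3.3 states: "We should collect the blood and stool samples for urotoxins and intestinal flora measurements in the 12th week"; "We should record the diet of patients in the 12th week"; and "We should collect the results of recent routine blood test before dialysis of the patient in the 4th, 8th and 12th week". The same measures are also taken before treatment, at the introduction visit (section 3.3.3.2 and the flowchart).

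Section 3.4.2 lists urotoxins, flora, biochemistry and dietary intake as secondary outcomes. Of the product, section 3.5 says: "It can regulate intestinal flora, improve nutritional status, reduce serum levels of urotoxins and improve quality of life".

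**The concern.** Selecting covariates by their univariate P-value or by association with the outcome is a habit of observational risk-factor studies. In a randomised comparison it has two consequences.

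First, the model is not fixed in advance. Which variables enter, and so what the treatment coefficient is adjusted for, depends on the data and can differ for each of the several primary scales. This holds even if only baseline values are considered.

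Second, with no time limit, a value measured under treatment can qualify. If treatment changes that value and the value affects the outcome, conditioning on it takes the indirect part of the effect out of the treatment coefficient. The coefficient then no longer estimates the effect of being assigned the product. The protocol's own reasoning makes such variables plausible candidates: section 3.5 expects flora and urotoxins to change along with nutrition and quality of life, and the background describes flora imbalance, toxin accumulation and malnutrition as a cycle.

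At stake is whether a product that works could look weaker, or null, for a purely analytic reason.

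**Working it through.** The plan gives no figure on this point to reproduce. The one design figure used is the sample size in section 3.6: 30 per group with 20% dropout leaves 30 × 0.8 = 24 per arm. (The step from 20 to 30 per group does not itself reproduce, since 20 / 0.8 = 25. The plan errs on the larger side, and this does not bear on the present point.)

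**1. Chance selection, even with baseline values only.** Section 3.4.2 lists 13 routine biochemical indicators and 3 urotoxins, 16 candidates in all. If none were related to the outcome and they were independent (an assumption), the screen would admit 16 × 0.1 = 1.6 on average, and at least one with probability 1 − 0.9^16 = 0.81, per outcome. In a linear model such baseline noise variables do not bias the treatment estimate. They make it depend on the data.

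**2. Shrinkage if an on-treatment mediator qualifies.** Assumptions, none from the protocol: total effect 0.80 SD; mediator M = 0.8 × arm + N(0,1); outcome = 0.6 × baseline + m × M + 0.8 × (1 − m) × arm + residual, where m is the mediated share. With M in the model, the arm coefficient is 0.8 × (1 − m). The simulation applies the P<0.1 screen to M, with 24 per arm.

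| Mediated share m | 10% | 30% | 50% | 70% |
|---|---|---|---|---|
| 0.8 × (1 − m), M always in | 0.72 | 0.56 | 0.40 | 0.24 |
| Simulated mean under the screen | 0.73 | 0.58 | 0.40 | 0.24 |

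The simulated mean is slightly higher at small shares because M sometimes fails the screen. At 30% mediated it passes in 79–89% of trials, depending on the residual variance. The shrinkage is close to a restatement of the assumed share.

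**3. Power.** This depends strongly on the residual variance. Power without M can be approximated by Φ(0.8 / (s × √(2/24)) − 1.96), where s is the SD of the outcome given arm and baseline, and √(2/24) = 0.289.

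- *Outcome variance given arm fixed at 1.* Residual variance is 1 − 0.36 − m², that is 0.55, 0.39 and 0.15 at m = 30%, 50% and 70%. Then s = √0.64 = 0.80, giving Φ(3.46 − 1.96) = 93% (simulated about 91%). Under the rule: 66%, 52% and 49%.
- *Residual variance fixed at 1.* Then s = √(1 + m²) = 1.04, 1.12 and 1.22, giving about 76%, 70% and 62% without M. Under the rule: 43%, 24% and 13%.
- *A second model without a baseline term* (within-arm SD 1, mediator-outcome correlation 0.3 or 0.5), 24 per arm: 77% without M; under the rule 53–61%, 23–31% and 8–11% at 25%, 50% and 75% mediated. With 30 per arm: 86% without M, then 61–73%, 28–38% and 9–11%.

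At 50% mediated and 24 per arm, power under the rule therefore lies anywhere from 23% to 52%.

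**4. Logistic check.** Section 3.8 names logistic and Cox models, whereas steps 2 and 3 are linear. With a dichotomised outcome, 30 per arm and correlation 0.5, the mean log odds ratio falls from 1.34 to 0.82 at 50% mediated (power 71% to 26%), and from 1.32 to about zero at 100% (power 68% to 5%). The direction is the same. The fall need not be proportional, because odds ratios change scale when a covariate is added. No Cox check was made; the protocol defines no time-to-event outcome.

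**The case against.** The strongest reply is that section 3.8 never says week-12 variables will be covariates. It names general clinical data, outcome-associated variables and a screen. Urotoxins, flora, diet and laboratory values are all measured at baseline too, so the sentence can be read as meaning baseline values. This stands. A reader might infer that the plan intends to adjust for on-treatment mediators, but the text does not support that; it only fails to exclude it.

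A second reply is that the multivariate model is not the analysis of the trial. Univariate regression and unadjusted tests are planned beside it, and the primary outcomes are changes in scales and physical findings, which suit those tests better than logistic or Cox regression. This also stands. A reader might infer that the trial's result rests on the adjusted model, but nothing says so. Equally, no analysis is designated primary, so nothing prevents the adjusted estimate from being the one reported.

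Third, section 3.5 lists effects side by side and does not say that the product works *through* urotoxins or flora. It does not mention diet, albumin or C-reactive protein. Mediation is plausible from section 3.5 and the background together, most clearly for flora and urotoxins, but its share is unknown.

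Finally, the details could be left to a SAP. This reply does not stand against the rule itself: the protocol states the selection method, and an outcome-driven screen is a poor choice at either time point.

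**Conclusion.** The point holds in a limited form and should be fixed. Section 3.8 fixes an outcome-driven, P-value-based covariate rule for the exposure-outcome models and does not confine it to pre-randomisation values. It certainly makes the adjusted estimate depend on the data. Over-adjustment for on-treatment values is a possibility that the rule allows.

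If that happens, the adjusted estimate shrinks roughly in proportion to the mediated share, for example from 0.80 to about 0.58 SD at 30% and 0.40 SD at 50%. This rests on an assumed effect of 0.80 SD, a single mediator and a linear model. Power falls in every setting from 25% mediated upwards, but no single power figure is defensible.

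The unadjusted comparisons are not touched, and section 3.6 describes the trial as exploratory, so this is not an error in a designated primary analysis.

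**What to change.** Replace the selection sentence in section 3.8 with wording such as:

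> The adjusted model for the treatment effect includes treatment arm, the baseline value of the outcome and a short list of pre-randomisation variables named before the data are seen. No post-randomisation variable, and no variable chosen by a univariate P-value, enters this model.

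How short the list is remains the sponsor's choice; with about 24 to 30 patients per arm it should be very short. Associations with on-treatment urotoxins, flora, diet or laboratory values can be reported separately, labelled as exploratory mechanism analyses.

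The cost is a change of wording in one section. No new data, patients or procedures are needed. The downside is that the exploratory risk-factor models move to a section of their own.
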